3.4.1 Vital Signs

Vital signs will be obtained and recorded at the Day 1 Visit, prior to the first administration of the test medication (placebo/ study drug) and on week 2, week 4, week 6, week 8 and week 10. The following vital signs will be measured: 1) blood pressure measurements (mm Hg) will be taken while the subject is relaxed in a sitting position for at least 3 minutes with the arm at heart level. 2) Heart rate will be measured via auscultation of the heart or palpation of a peripheral pulse and will be recorded in beats per minute (bpm). 3) Oral temperature will be recorded in degrees Fahrenheit (^oF). Subjects with an oral temperature less than (\leq) 99.6^oF (37.4^oC) may continue.

Clinically significant negative changes from baseline will be recorded on the adverse event forms.

3.4.2 Ophthalmic Examination

At all visits, the Investigator will conduct a complete undilated examination of the eyes using a binocular slit lamp. The Investigator will examine the tear film, eye lids, lashes, bulbar and palpebral conjunctiva, upper and lower lid puncta, cornea, anterior chamber, iris, lens, and anterior vitreous. Specific signs that will be recorded include: lacrimal sac area erythema, swelling or tenderness; froth or debris or mucous strands in tear film; eyelid hyperemia; punctal hyperemia or atresia; conjunctival/ episcleral hyperemia; papillary or follicular conjunctival reaction; chemosis, episcleral edema; superficial punctate keratopathy, corneal scar, corneal neovascularization; presence and number of corneal filaments, presence or absence of mucoid films, anterior chamber cell, flare or KPs; pupil shape abnormalities,

anterior or posterior synechiae, iris neovascularization; lenticular opacities; vitreous cells or pigment. Conjunctival hyperemia (ocular surface redness) will be graded at each visit using the VBR grading system as explained in section 3.2.5. Measurements at first and last visit will include: visual acuity (BCSVA), manifest refraction and intraocular pressure measurement. Clinically significant changes from baseline examination will be recorded on the adverse event forms.

4 Subject Selection and Withdrawal

4.1 Inclusion Criteria

Patients will be eligible for the study if all of the following criteria are met:

1. Aged 18 years or older.
2. Capable of giving informed consent and does provide informed consent.
3. Documented Dry Eye Disease for at least 6 months.
4. Schirmer I <10
5. Corneal/ conjunctival (Rose Bengal) staining ≥ 1
6. Ocular symptoms must be considered as annoying or activity limiting (OSDI ≥ 13 ; mild).
7. Women must be post-menopausal ≥ 1 year, or surgically sterilized. If not, a negative urine pregnancy test is required within 14 days of receiving her first dose of test medication (placebo/ study drug) along with definite evidence of contraceptive use during the duration of the study. Women of reproductive age should use a method of birth control that is acceptable to the subject and the study doctor. This may include oral contraceptive pills, birth control implants, barrier methods or abstinence. If a subject mentions she suspects she may be pregnant after being enrolled, another pregnancy test will be administered. If the test is positive, she will be discontinued from the study immediately.

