6.5.3	Visit 3: Week 2 (\pm 2 days)	25
6.5.4	Visit 4: Week 4 (\pm 2 days)	25
6.5.5	Visit 5: Week 6 (\pm 2 days)	26
6.5.6	Visit 6: Week 8 (\pm 2 days)	26
6.5.7	Visit 7: Week 10 (\pm 2 days)	26
7	STATISTICAL PLAN	26
7.1	SAMPLE SIZE DETERMINATION	26
7.2	STATISTICAL METHODS	27
7.3	SUBJECT POPULATION(S) FOR ANALYSIS	27
8	SAFETY AND ADVERSE EVENTS	27
8.1	ADVERSE EVENT DEFINITIONS	27
8.2	CLASSIFICATION OF ADVERSE EVENTS BY SEVERITY	28
8.3	CLASSIFICATION OF ADVERSE EVENTS BY RELATIONSHIP TO STUDY TREATMENT	28
8.4	ACTION(S) TAKEN	29
8.5	OUTCOME	29
8.6	ADVERSE EVENT REPORTING	29
8.7	SERIOUS ADVERSE EVENT REPORTING	29
8.8	IN CASE OF AN EMERGENCY	30
8.9	DATA SAFETY MANAGEMENT PLAN	30
8.10	STUDY OVERSIGHT	30
9	CONFIDENTIALITY	31
10	SOURCE DOCUMENTS	31
10.1	RECORDS RETENTION	31
11	ETHICAL CONSIDERATIONS	31
12	STUDY FINANCES	32
12.1	FUNDING SOURCE	32
12.2	CONFLICT OF INTEREST	32
12.3	SUBJECT STIPENDS OR PAYMENTS	32
13	REFERENCES	33

SCHEDULE OF VISITS AND PROCEDURES

	Screening	Day 1 (Pre-Dose)	Day 1 (Post-Dose)	Week 2	Week 4	Week 6	Week 8	Week 10
Informed Consent	X							
Demographic Information	X							
Medical History/Con Meds	X							
Ophthalmic/Dry Eye History	X							
Vital Signs		X		X	X	X	X	X
Ophthalmic Examination (Slit lamp)	X	X		X	X	X	X	X
Ocular surface redness score	X	X		X	X	X	X	X
Schirmer 1 test and Rose Bengal staining	X						X	
Pregnancy Test (urine)*	X							
Best Spectacle Corrected Visual Acuity		X						X
Randomization visit		X						
First Study Medication		X						
Drug dispensation visits			X	X	X	X		
Instruction on study medication self-administration			X					
Ocular Surface Disease Index (OSDI)		X		X	X	X	X	X
Visual Analogue Scale (VAS)			X	X	X	X	X	
Physical inspection of nose & oropharynx				X	X	X	X	X
Clinical Global Impression (CGI)		X		X	X	X	X	X
Subject Global Assessment (SGI)		X		X	X	X	X	X
Adverse Events/ Concomitant Medications		X	X ⁺⁺	X	X	X	X	X

*If applicable ++ AEs only

ABBREVIATIONS

AE	Adverse Event
APC	Antigen-presenting cells
BSCVA	Best Spectacle Corrected Visual Acuity
EC	Ethics Committee
eDNA	Extracellular DNA
CNL	Corneal Neurobiology Laboratory
CRF	Case Report Form
CGI	Clinical Global Impression
DCF	Data Clarification Form
DED	Dry Eye Disease
DNase I	Deoxyribonuclease I
FDA	Food and Drug Administration
FVC	Forced vital capacity
GCP	Good Clinical Practice
ICH	International Conference on Harmonization
IB	Investigator's Brochure
IOP	Intraocular pressure
IRB	Institutional Review Board
KCS	Keratoconjunctivitis sicca

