3.2.1 Efficacy End Point: Ocular Surface Disease Index (OSDI)

The OSDI rating scale has twelve questions in three discrete areas, with responses rated on a five point scale. Subjects will complete this scale on Day 1 prior to first dose (Baseline), week 2, week 4, week 6, week 8 and week 10. The questions and scoring system are shown below:

HAVE YOU EXPERIENCED ANY OF THE FOLLOWING DURING THE LAST WEEK:

	All of the time	Most of the time	Half of the time	Some of the time	None of the time
1. Eyes that are sensitive to light?	4	3	2	1	0
2. Eyes that feel gritty?	4	3	2	1	0
3. Painful or sore eyes?	4	3	2	1	0
4. Blurred Vision?	4	3	2	1	0
5. Poor vision?	4	3	2	1	0

HAVE PROBLEMS WITH YOUR EYES LIMITED YOU IN PERFORMING ANY OF THE FOLLOWING DURING THE LAST WEEK:

	All of the time	Most of the time	Half of the time	Some of the time	None of the time	
6. Reading?	4	3	2	1	0	N/A
7. Driving at night?	4	3	2	1	0	N/A
8. Working with a computer Or bank machine (ATM)?	4	3	2	1	0	N/A
9. Watching TV?	4	3	2	1	0	N/A

HAVE YOUR EYES FELT UNCOMFORTABLE IN ANY OF THE FOLLOWING SITUATIONS DURING THE LAST WEEK:

	All of the time	Most of the time	Half of the time	Some of the time	None of the time	
10. Windy conditions?	4	3	2	1	0	N/A
11. Places or areas with Low humidity (very dry)?	4	3	2	1	0	N/A
12. Areas that are air conditioned?	4	3	2	1	0	N/A

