5.3 Method for Assigning Subjects to Treatment Groups

This Randomized placebo-controlled trial will have two study groups. Subjects will be randomly assigned to one of two groups (#1, #2). Group #1 will receive placebo (drug vehicle; control group) and Group #2 will receive study drug (rhDNase 0.1%; test group). We will use a computer-based random code generator (Research Randomizer; <http://randomizer.org/>) to generate 1 set of 72 non-unique, unsorted numbers with a range from 1 to 2 representing the group number (#1 is control group, #2 is test group). Each subject will be assigned a study identification (ID) number at screening, eg. subject #1, subject #2, subject #3 and so on. Based on the randomizer generated table, subject #1 will receive either placebo (#1 group) or study drug (#2 group). This will be repeated for each subject. For reproducibility purpose, we will document the final randomization schedule and the random SEED number used to generate the schedule. Randomization will be performed by the Illinois Eye and Ear Infirmary's pharmacy, and neither participants nor research staff will be aware of the assigned treatments. The person conducting the randomization will remain masked as well.

The study identification (ID) number will be used on all study-related documents. To maintain confidentiality, the subject's name will not be recorded on any study document other than the informed consent form. The drug vial number will be linked to the patient identification number.

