5.6 Prior and Concomitant Therapy

Prior medications are defined as all medications taken within 30 days prior to Day 1, whether there is continued use or not. Concomitant medications must be identified in the patient's medical record, including all lubricants administered for Dry Eye Disease. These medications will be recorded in the case report form (CRF).

• For each medication taken, the following information will be collected:

1. Medication trade name
2. Eye that was treated, if applicable
3. Indication for which the medication was given

4. Date started
5. Date stopped
6. Dose of medication used.

There will be a 2-week washout period of topical corticosteroids and topical cyclosporine before enrollment and these medications are prohibited throughout the study. Other than these, participants will be permitted to continue their chronic DED treatments which include the use of artificial tears, eyelid massage, or warm compresses. The number of drops and frequency must be recorded in the patient diary provided.

- The use of any investigational agent during past 30 days is prohibited.

There is only one FDA approved treatment currently available to treat patients with Keratoconjunctivitis Sicca (dry eye disease)- Cyclosporine 0.05% (marketed as Restasis). The FDA approved indication for Restasis use is the following: “to increase tear production in patients whose tear production is presumed to be suppressed due to ocular inflammation associated with keratoconjunctivitis sicca”. Restasis will be withheld during the course of this study. This is necessary as the proposed mechanism of action of rhDNase in dry eyes is to reduce inflammation on the surface of the eye. Restasis can also reduce inflammation albeit via a different mechanism. Thus, because of over lapping anti-inflammatory actions, it may not be possible to attribute any observed clinical benefit to rhDNase treatment if Restasis is used concurrently. This approach has been used in other clinical trials that have investigated the use of an anti-inflammatory agent in dry eye disease.³²

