6.1 Patient Recruitment and Screening

Prior to recruitment of any patients into the study, written approval of the protocol and informed consent will be obtained from the Institutional Review Board (IRB).

Potential subjects will be recruited from the clinical practice of the investigator at the time of their eye examination visit. The clinical practice is located at the Department of Ophthalmology and Visual Sciences, Eye and Ear Infirmary, [name]. Patients with established Dry Eye Disease (for at least 6 months with annoying or activity limiting visual symptoms) will be approached by a member of the research staff to determine if the patient might be interested in participating in a research study. If the patient is interested, the research staff member will describe the study. If the patient is willing to enter the study, the study will be discussed and the patient will be asked to sign the informed consent form. Consent will be obtained prior to screening to determine eligibility. Subjects will be screened for eligibility, as per the inclusion/ exclusion criteria, and as detailed in section 6.5.1. Eligible patients will be enrolled in the study.

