6.5.1 Visit 1 Screening

Day -18 to 0

After obtaining informed consent, the following assessments will be performed within fourteen days prior to the subject receiving the first dose of study medication:

- Demographic information including: birth date, gender, race or ethnic origin.
- Medical History including prior medication use and prior procedures: Medical history will be obtained by interviewing the subject and will include a review of the following systems: cardiovascular, dermatologic, gastrointestinal, genitourinary, musculoskeletal, neurologic and respiratory. An allergic history (including medications and food), substance abuse history (including alcohol) and a history of medication use (including prescription, OTC, and herbal products) during the past 30 days will also be completed.
- Ophthalmic and Dry Eye Disease history including: date when the Dry Eye Disease began, verification that the subject has had Dry Eye Disease for at least 6 months, medications used by the subject to treat Dry Eye Disease, previous procedures to treat Dry Eye Disease.
- Ophthalmic Examination (slit lamp examination, Ocular surface redness score, Rose Bengal staining, and a Schirmer 1 test)
- Pregnancy test (urine), if applicable. Women of reproductive age will be asked to use a method of birth control that is acceptable to the subject and the study doctor. This may include oral contraceptive pills, birth control implants/shots or patches, barrier methods or abstinence. Women of reproductive age will not be included in the study if they refuse to use any birth control measure, including abstinence.

Patients currently treating DED with corticosteroids and/or Restasis will stop these treatments during a wash-out period (2 weeks before the start the study drug) and during the whole study. The study doctor will provide advice about decreasing DED symptoms with artificial tears, eyelid massage, or warm compresses.

If the patient agrees to enter the study, the first treatment visit will be scheduled. If a washout period is needed, Visit 2 will be after 2 weeks (\pm 4 days). If a washout period is not necessary, Visit 2 can be scheduled any time in the next 2 weeks after the Screening Visit.

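### OSDI ≥ 13 is an entry criterion, but no OSDI is collected at screening: either the score is unchecked when eligibility is decided, or the Day 1 baseline doubles as the selection score

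*Combined protocol and SAP*

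**What the plan says.** Criterion 6 in section 4.1 sets a numeric threshold: "Ocular symptoms must be considered as annoying or activity limiting (OSDI ≥ 13 ; mild". The Study Summary repeats it.

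Section 6.1 says when eligibility is settled: "Subjects will be screened for eligibility, as per the inclusion/ exclusion criteria, and as detailed in section 6.5.1". Section 4.3 also refers to section 6.5.1 for the screening assessments.

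The eye assessments in section 6.5.1 are "Ophthalmic Examination (slit lamp examination, Ocular surface redness score, Rose Bengal staining, and a Schirmer 1 test". These cover criteria 4 and 5 (Schirmer I and Rose Bengal). OSDI is not listed.

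The schedule row "Ocular Surface Disease Index (OSDI" has a blank Screening cell and its first mark under Day 1 (Pre-Dose). Section 3.2.1 agrees: "Subjects will complete this scale on Day 1 prior to first dose (Baseline". So does the Visit 2 list in section 6.5.2.

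On sequence, section 6.5.1 says "If a washout period is needed, Visit 2 will be after 2 weeks", and section 5.6 says "There will be a 2-week washout period of topical corticosteroids and topical cyclosporine before enrollment". Section 5.3 says "Each subject will be assigned a study identification (ID) number at screening", and that number points to a row of a fixed list of 72 treatment codes.

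The Study Summary makes OSDI change from Baseline to Week 8 the primary efficacy measure. The only test that section 7.2 names for OSDI is a Wilcoxon signed-rank test of baseline against each later visit. The same section also promises 95% confidence intervals for drug against placebo.

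**The concern.** A numeric inclusion criterion needs a measurement at the point where it is applied, and the plan schedules none there. Staff who follow it literally must take one of two routes.

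- **Unscored entry.** Subjects pass screening on a verbal impression of bothersome symptoms. The threshold is not checked against a score at that decision, and a subject below 13 can reach the randomisation visit.
- **Selection on Day 1.** The threshold is applied to the pre-dose Day 1 score. This conflicts with sections 4.3 and 6.1. Subjects who needed washout have by then stopped their topical corticosteroid or cyclosporine for about two weeks. The ID tied to the list has already been issued. The score that admits a subject is also the baseline for the primary measure.

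The second route has a statistical cost. Admitting only subjects whose baseline exceeds a cut-off favours those whose score is high by chance on that day. Their later scores drift down without treatment, and a baseline-to-follow-up test reads the drift as improvement.

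**Working it through.** **1. Where OSDI appears.**

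| Place | OSDI at screening? | OSDI on Day 1 pre-dose? |
|---|---|---|
| Schedule of visits | No (blank cell) | Yes |
| Section 3.2.1 | No | Yes, as Baseline |
| Section 6.5.1 (Visit 1) | Not listed | n/a |
| Section 6.5.2 (Visit 2) | n/a | Yes |

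The four places agree, so a table broken in conversion does not explain the gap. No separate OSDI for eligibility is planned. Section 6.5.2 does not give the order of OSDI scoring and randomisation within Visit 2.

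**2. Regression to the mean if Day 1 OSDI selects.** The plan has no figure to reproduce. Assume OSDI is normal with mean m and SD s among patients approached, with correlation r between Day 1 and follow-up and no treatment effect. With z = (13 − m)/s, the expected fall in each arm is

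(1 − r) × s × φ(z) / (1 − Φ(z)).

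Only the 13 comes from the protocol; m, s and r are assumptions.

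| m / s | z | s × φ(z)/(1 − Φ(z)) | r = 0.7 | r = 0.8 | r = 0.9 |
|---|---|---|---|---|---|
| 25 / 15 | −0.80 | 15 × 0.2897/0.7881 = 5.51 | 1.65 | 1.10 | 0.55 |
| 30 / 20 | −0.85 | 20 × 0.2780/0.8023 = 6.93 | 2.08 | 1.39 | 0.69 |
| 40 / 20 | −1.35 | 20 × 0.1604/0.9115 = 3.52 | 1.06 | 0.70 | 0.35 |

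The range is 0.35 to 2.08 points. A lower assumed mean of 20 with SD 15 gives 0.79 to 2.37.

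**3. Effect on the tests.** For m/s of 20/15, 30/20 and 40/20 and the same three values of r, 4,000 trials per setting were simulated with 30 subjects per arm and no treatment effect, at two-sided 0.05.

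| Comparison | Rejection rate over the settings |
|---|---|
| Within-arm signed-rank, Day 1 score selects and is baseline | 0.054 to 0.174 |
| Between-arm rank-sum on change, same selection | 0.046 to 0.055 |
| Within-arm signed-rank, separate screening score selects | 0.045 to 0.064 |

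The highest within-arm figure, 0.174, belongs to 20/15 with r = 0.7. With 30/20 and 40/20 the range is 0.054 to 0.111. In the third row the differences are symmetric about zero by construction, so values above 0.05 are simulation error.

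**4. How far a separate screening score helps.** The third row assumes that screening OSDI correlates equally with Day 1 and Week 8. If the correlations were 0.9 and 0.7 (assumed), the 30/20 case would keep (0.9 − 0.7) × 6.93 = 1.39 points, against (1 − 0.7) × 6.93 = 2.08 when Day 1 selects.

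**5. List rows.** If 5%, 10% or 20% (assumed) of the 72 listed IDs failed on Day 1 and were not replaced, 72 × 0.95 = 68.4, 72 × 0.90 = 64.8 or 72 × 0.80 = 57.6 treated subjects would remain. Section 7.1 wants at least 30 completers per group. The only replacement rule found, in section 8.1, is for withdrawals due to adverse events.

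**The case against.** Several counter-arguments stand and limit the point.

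- **A reader might infer that eligibility is decided on Day 1.** No section says so. Section 6.1 points to screening, and sections 4.3 and 6.1 pre-select on symptoms in words close to those of criterion 6. The documents establish that the threshold and its measurement are not aligned; Day 1 selection is one of two possible consequences.
- **A reader might infer that the treatment comparison is biased.** It is not. The regression acts equally in both randomised arms, and the simulated between-arm rates are nominal. The within-arm test is also a weak basis for an efficacy claim whenever OSDI is scored.
- **A reader might infer that ineligible subjects will necessarily be dosed.** OSDI is listed before the first dose, and section 5.3 keeps participants and research staff unaware of assignment. A subject below 13 can be stopped undosed and masked, which would not be expected to bias the arms.
- **Washout is not universal.** It applies only to users of topical corticosteroids or cyclosporine. Exclusion 6 already means that their final eligibility cannot be settled before washout ends.
- **The choice of score is arguable.** OSDI asks about the past week. In current users of those drugs a Visit 1 score reflects symptoms on therapy, and a Day 1 score symptoms off it. Selecting at Visit 1 could leave out users whose symptoms are controlled.
- **Lost list rows are not specific to OSDI.** IDs are issued at the visit where Schirmer and Rose Bengal are done, so any screen failure can use up a row. Moving OSDI does not cure that.

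None of this supplies the missing measurement or reconciles sections 4.1, 4.3, 6.1 and 6.5.1 with the schedule.

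**Conclusion.** The inconsistency is in the text and needs no assumption: criterion 6 carries a numeric threshold, eligibility is assigned to screening, and no OSDI is taken there. As written, the threshold is either unchecked when eligibility is decided or applied to the score that serves as baseline.

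The statistical harm is conditional and modest. If Day 1 selects, each arm shows an untreated fall of about 0.35 to 2.1 OSDI points, and the planned within-arm test rejects too often. Those sizes rest on an assumed normal distribution, assumed means and SDs, and r between 0.7 and 0.9. The randomised comparison between drug and vehicle is unaffected. The list-row problem is real but arises from issuing list-linked IDs at screening, so it needs its own correction. The point should be corrected, but it does not undermine the design.

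**What to change.** 1. Reconcile sections 4.1, 4.3, 6.1, 6.5.1 and the schedule: add OSDI to Visit 1 and state that this score decides criterion 6.
2. Keep the Day 1 pre-dose OSDI as baseline for change only, with no role in selection.
3. Base the efficacy conclusion on the between-arm comparison of OSDI change, and treat within-arm tests as descriptive.
4. Separately, amend section 5.3 so that rows of the 72-number list go to subjects confirmed eligible and randomised at Visit 2. IDs can still be given at screening. A failure on any criterion then uses up no row.

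The cost is one 12-item questionnaire at a visit that already takes place. Three downsides should be stated in the protocol. Some subjects will score below 13 on Day 1 and stay in. In subjects who need washout, the qualifying score reflects symptoms on therapy. Some regression to the mean may remain if screening OSDI tracks Day 1 more closely than Week 8, which is a further reason for item 3.

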4.2 Exclusion Criteria

Subjects will not be eligible for the study if any of the following criteria are met:

1. Allergic to rhDNase1 or any similar products, or excipients of rhDNase1 eye drops 0.1%.
2. Receiving or have received within 30 days any experimental systemic medication.
3. Active ocular infection or ocular allergies.
4. Any history of eyelid surgery or ocular surgery within the past 3 months.
5. Corneal epithelial defect larger than 1 mm² in either eye.
6. The use of topical cyclosporine or corticosteroids within 2 weeks of enrollment
7. Are homeless.
8. Have active drug/alcohol dependence or abuse history.

Except for a 2-week washout period of topical corticosteroids and topical cyclosporine before enrollment, participants will be permitted to continue their other chronic treatments, including the use of artificial tears, eyelid massage, or warm compresses.

